- Randomization/Day 1 may occur any time after Screening laboratory results are available and reviewed by the Investigator.
-  All subsequent visits and week increments should be based on the date of Visit 2. All visit windows are ±3 days for subsequent visits.
-  Also serves as the Early Termination Visit for patient withdrawal in this period.
-  The Safety Follow-Up Visit is intended for those patients who do not roll over into an openlabel extension and for patients who have been discontinued from the study and completed the Early Termination Visit (Week 24).
-  For females of childbearing potential, a serum pregnancy test will be performed at all visits aside from the randomization visit where a urine pregnancy test will be performed.

-  If PPD (skin test) is performed, subject will need to return to the clinic 24-48 hours after placement for PPD reading.
-  Includes hematology and serum chemistry.
-  When possible, collect pre-dose, except on Visit 11.
-  Will include thyroid stimulating hormone and hemoglobin A1c at Screening only.
-  Includes total cholesterol, low-density lipoprotein, high-density lipoprotein, and triglycerides.
- 11 Should be performed by the same rater, when possible, for the patient for the duration of the study.
-  For participants who authorize photographs to be taken of their scalp involvement and/or eye and nail involvement.
- Will be conducted at Visit 6 (Week 8) only.
- 14 Error! Reference source not found. Collection is ongoing.

2.	TABLE OF CONTENTS, LIST OF TABLES, AND LIST OF FIGURES			
1.	SYNOPSIS	7		
2.	TABLE OF CONTENTS, LIST OF TABLES, AND LIST OF FIGURES	16		
3.	LIST OF ABBREVIATIONS AND DEFINITIONS OF TERMS	21		
4.	INTRODUCTION	23		
4.1.	Overview of Alopecia Areata	23		
4.2.	Rationale for the Study	23		
4.2.1.	Scientific Rationale	23		
4.3.	Preclinical Information for CTP-543	25		
4.4.	Clinical Information	25		
4.4.1.	Clinical Studies of CTP-543	25		
5.	ETHICS	28		
5.1.	Institutional Review Board (IRB)	28		
5.2.	Written Informed Consent	28		
6.	STUDY OBJECTIVES	29		
6.3	Study Design	29		
6.4	Method of Treatment Assignment	30		
7.	SELECTION AND WITHDRAWAL OF PATIENTS	31		
7.1.	Patient Inclusion Criteria	31		
7.2.	Patient Exclusion Criteria:	32		
7.3.	Patient Withdrawal Criteria	34		
7.3.1.	Patient Withdrawal Procedures	34		
7.4.	Criteria for Study Termination	35		

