#### 10. ADVERSE EVENTS

#### 10.1. Definition of Adverse Event

An adverse event is any untoward medical occurrence that may appear or worsen in a patient during the course of a study. It may be a new intercurrent illness, a worsening concomitant illness, an injury, or any concomitant impairment of the patient's health, including laboratory test values, regardless of etiology. Any worsening (i.e., any clinically significant adverse change in the frequency or intensity of a pre-existing condition) should be considered an adverse event. A diagnosis or syndrome should be recorded on the adverse event page of the eCRF rather than the individual signs or symptoms of the diagnosis or syndrome. A worsening of the condition under study, alopecia areata, will not be reported as an adverse event.

All patients will be monitored for adverse events during the study. Assessments may include monitoring of the following parameters: the patient's clinical symptoms, laboratory, physical examination findings, or findings from other tests and/or procedures.

An adverse event reported after informed consent, but before the first dose of study drug (i.e., Day 1), will be considered a pretreatment adverse event and will be captured on the eCRF. Adverse events will be considered treatment-emergent if the onset is after the first dose of study drug or if an ongoing Adverse Event worsens after dosing is initiated.

Laboratory results deemed Abnormal and clinically significant by the investigator will be recorded as an adverse event in the eCRF and should be fully investigated and repeated for verification.

Regardless of severity grade, only laboratory abnormalities that fulfill a seriousness criterion need to be documented as a serious adverse event.

If a laboratory abnormality is one component of a diagnosis or syndrome, then only the diagnosis or syndrome should be recorded on the adverse event eCRF. If the abnormality was not a part of a diagnosis or syndrome, then the laboratory abnormality should be recorded as the adverse event. If possible, the laboratory abnormality should be recorded as a medical term and not simply as an abnormal laboratory result (e.g., record thrombocytopenia rather than decreased platelets).

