### **10.6.** Reporting Adverse Events

The Investigator must report to Sponsor or its designee all adverse events that occur during the study from the time written informed consent is given until the final study visit or early termination, regardless of their relationship to the study drug. Serious adverse events and pregnancies will be reported from the time written informed consent is given through 30 days beyond the last dose of study drug.

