#### **Adverse Events**

An adverse event reported after informed consent, but before the first dose of study drug (i.e., Day 1), will be considered a pre-treatment adverse event. Treatment-emergent adverse events (TEAEs) will be defined as any adverse event that occurs after administration of the first dose of study drug until Week 24 or the Early Termination Visit. The number and percentage of patients who report TEAEs will be summarized by system organ class and preferred term.

Treatment emergent adverse events will also be summarized by intensity as well as relationship to study drug.

Patients who report the same preferred term on multiple occasions will be counted once for the preferred term: under the highest severity when summarized by severity and under the closest relationship to study drug when summarized by relationship. If a patient reports multiple preferred terms for a system organ class, the patient will be counted only once for that system organ class.

The number and percentage of patients who experience TEAEs will be summarized by dosing regimen for the following:

- By system organ class and preferred term
- By severity/intensity, system organ class, and preferred term
- By relationship to study drug, system organ class, and preferred term
- Serious adverse events by system organ class and preferred term
- Serious adverse events by relationship to study drug, system organ class, and preferred term
- Adverse events resulting in discontinuation of study drug by system organ class and preferred term
- Adverse events that result in study drug dose interruption by system organ class and preferred term

By-patient listings will be provided for any deaths, serious adverse events, and adverse events leading to discontinuation of treatment.

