3.4 Changes to the Analysis from the Protocol

The Efficacy analysis population described in the synopsis of the protocol is referred to as the modified Intent-to-Treat (mITT) analysis population in Section 11.3 of the protocol. To avoid confusion, this analysis population will be called the mITT analysis population in this SAP as well as in the statistical outputs.

As per Section 11.4.3 of the protocol, the total number of days on study drug will exclude dose interruptions. However, dose interruptions will not be excluded from the duration of exposure to the study drug as specified in Section 11, in order to be in line with industry's standards.

	STATISTICAL ANALYSIS PLAN, Final v1.0
Protocol Number CP543.2003	Sponsor: Concert Pharmaceuticals, Inc.

As per Section 11.4.4 of the protocol, treatment-emergent AEs (TEAEs) are defined as any AE that occurs after administration of the first dose of study drug until Week 24 or Early Termination Visit. However, TEAEs will be defined as any AEs with onset date/time on or after the first dose of study drug (refer to Section 13.1), in order to be in line with the industry's standards.

As per Section 11.4.4 of the protocol, the number and percentage of patients with abnormal, clinically significant laboratory values (per Investigator judgment) will be summarized by dosing regimen for each clinical laboratory variable. This summary has been replaced by shift tables from Baseline to the worst post-Baseline result describing shifts to abnormality as assessed by the central laboratory (low, normal, high) (refer to Section 13.2). Abnormal, clinically significant laboratory values (per Investigator judgement) will be identified in by-patient data listing.

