13.1 Adverse Events

AEs will be coded according to the MedDRA, version 22.0.

An AE reported after informed consent, but before the first dose of study drug (i.e., Day 1), will be considered a pre-treatment adverse event.

TEAEs are defined as any AEs with onset date/time on or after the first dose of study drug. See Appendix 3 for handling of completely or partially missing dates for AEs. In the case where it is not possible to define an AE as treatment emergent or not, the AE will be classified as treatment emergent.

An overall summary table of AEs will be provided. The frequency and percentage of patients who experienced at least one AE, TEAE, TEAE by greatest relationship with study drug, TEAE by highest severity/intensity, serious TEAE, treatment-related serious TEAE, TEAE leading to study drug discontinuation, TEAE leading to study drug dose interruption, TEAE leading to study discontinuation, and TEAE leading to death will be presented.

Frequency and percentage of patients who experienced TEAE will be summarized by SOC and PT. A patient experiencing multiple TEAEs within the same SOC will be counted only once for that SOC. Similarly, a patient experiencing multiple TEAEs within the same PT will be counted only once for that PT. TEAEs will be sorted alphabetically by SOC and PT will be presented by decreasing order of total frequency within each SOC. Serious TEAEs and treatment-related serious TEAEs will be summarized similarly.

Frequency and percentage of patients who experienced TEAE will be further broken down by greatest relationship to study drug. A treatment-related AE is defined as any TEAE that is assessed by the Investigator as definitely, probably or possibly related to study drug. A not related TEAE is defined as any TEAE that is assessed by the Investigator as unlikely related or not related to the study drug. TEAE with an unknown/missing relationship to study drug will be considered as treatment related. A patient experiencing multiple TEAEs within the same SOC will be counted only once for that SOC under the greatest relationship to study drug. Similarly, a patient

	STATISTICAL ANALYSIS PLAN, Final v1.0			
Protocol Number CP543.2003	Sponsor: Concert Pharmaceuticals, Inc.			

experiencing multiple TEAEs within the same PT will be counted only once for that PT under the greatest relationship to study drug.

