14 APPENDICES

Appendix 1

Table 1 provides a description of the procedures planned at each visit.

	STATISTICAL ANALYSIS PLAN, Final v1.0
Protocol Number CP543.2003	Sponsor: Concert Pharmaceuticals, Inc.

Table 1: Schedule of Events

	Screening	Randomization ¹ Day 1 ² (Visit 2)	Treatment Period					Safety Follow-Up
Event	Day -28 to Day -1 (Visit 1)		Week 2, 6 (Visit 3, 5)	Week 4, 8 (Visit 4, 6)	Week 12 (Visit 7)	Week 16, 20 (Visit 8, 9)	Week 24 ³ /ET (Visit 10)	Week 28 ⁴ (Visit 11)
Informed consent	X							
Eligibility assessment	X	X						
Demographics	X							
Medical and surgical history	X	X						
Randomization		X						
Physical examination	X	X					X	X
Brief physical examination				X	X	X		
Height	X							
Weight	X	X		X	X	X	X	X
Pregnancy test ⁵	X	X	X	X	X	X	X	X
Tuberculosis test ⁶	X							
Clinical laboratory testing ⁷⁸	X ⁹	X	X	X	X	X	X	X
Lipid assessment ¹⁰		X			X		X	X
HBV and HCV test	X							
12-lead electrocardiogram	X	X			X		X	X
Vital signs	X	X		X	X	X	X	X
Severity of Alopecia Tool (SALT) assessment ¹¹	X	X		X	X	X	X	
Photographs ¹²	X	X			X		X	
Patient Satisfaction Questions	X	X		X^{13}	X		X	
Visual Analog Scale (VAS) for Eyebrows		X			X		X	
Clinical Global Impression of Severity	X	X		X^{13}	X		X	
Clinical Global Impression of Improvement				X ¹³	X		X	
Patient Global Impression of Severity	X	X		X^{13}	X		X	
Patient Global Impression of Improvement				X^{13}	X		X	
Study Product Administration at study site		X	X	X	X	X		
Dispense study drug		X		X	X	X		
Study drug accountability				X	X	X	X	
Adverse events ¹⁴	X	X	X	X	X	X	X	X
Concomitant medications ¹⁴	X	X	X	X	X	X	X	X

	STATISTICAL ANALYSIS PLAN, Final v1.0
Protocol Number CP543.2003	Sponsor: Concert Pharmaceuticals, Inc.

ET=Early termination; HBV= hepatitis B virus; HCV = hepatitis C virus; PPD = purified protein derivative.

- Randomization/Day 1 may occur any time after Screening laboratory results are available and reviewed by the Investigator.
- ² All subsequent visits and week increments should be based on the date of Visit 2. All visit windows are ±3 days for subsequent visits.
- ³ Also serves as the Early Termination Visit for patient withdrawal in this period.
- ⁴ The Safety Follow-Up Visit is intended for those patients who do not roll over into an open-label extension and for patients who have been discontinued from the study and completed the Early Termination Visit (Week 24).

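### The SAP's open-ended TEAE window gives patients who skip the extension up to four extra off-drug weeks, which can bias the BID–QD tolerability comparison if roll-over differs by regimen

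*SAP*

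**What the plan says.** **The TEAE window.** Protocol 11.4.4 (Adverse Events) defines a TEAE as "any adverse event that occurs after administration of the first dose of study drug until Week 24 or the Early Termination Visit". Protocol 10.1 is looser: "Adverse events will be considered treatment-emergent if the onset is after the first dose of study drug", or if an ongoing event worsens once dosing has begun. It states no end. SAP 3.4 restates the 11.4.4 rule and replaces it openly: "TEAEs will be defined as any AEs with onset date/time on or after the first dose of study drug", giving alignment with industry standards as the reason. SAP 13.1 repeats the new rule: "TEAEs are defined as any AEs with onset date/time on or after the first dose of study drug".

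**Who is observed after Week 24.** Protocol 10.5 records adverse events from consent to the final study visit. Table 1 schedules adverse-event collection at Week 28, and footnote 4 says who attends: "The Safety Follow-Up Visit is intended for those patients who do not roll over into an open-label extension", together with discontinued patients who completed the ET visit. Roll-over patients have no visit in this study after Week 24. Protocol 7.3.1 lets the sponsor waive the follow-up visit for some patients who stopped dosing before ET. SAP 7.1 counts as completers patients who attended Week 28, patients who rolled over, and patients who did neither.

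**How TEAEs are summarised.** SAP 13.1 uses the number and percentage of patients with an event, by regimen. It has no exposure-adjusted rate, no table limited to Week 24/ET and no post-treatment category. In contrast, SAP 13.2 and 13.5 include summaries of laboratory and QTcF abnormalities restricted to time on treatment.

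**Serious events.** Protocol 10.6 has them reported "through 30 days beyond the last dose of study drug".

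**The concern.** Tolerability is half of the study's overall objective, and no safety inference is planned, so readers will compare the raw TEAE percentages of the two regimens. A percentage of patients with at least one event is comparable between groups only over similar observation periods. Under the SAP definition, a completer who rolls over is observed for 24 weeks. One who does not, and who attends Week 28, is observed for 28 weeks, the last four off drug.

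Patients choose whether to roll over after 24 weeks' experience of response and tolerability. If the regimens differ in either, roll-over may differ too, and the regimen with fewer roll-overs is then watched for longer and shows more events. Even with equal roll-over, a table read as events on each regimen includes events that began after dosing stopped. The rule in Protocol 11.4.4 avoids both problems among completers.

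**Working it through.** **Durations.** The synopsis gives 4 weeks' screening, 24 weeks' treatment and 4 weeks' follow-up: 4 + 24 + 4 = 32, which reproduces its stated total of about 32 weeks. The extra post-baseline observation is 4/24 = 16.7%.

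**Inputs not in the documents.** The documents give no expected TEAE risk, no roll-over share and no off-drug event rate. All three are assumptions below. Arm size (about 30) is from the synopsis.

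**Formulas.** Let p be the 24-week risk of at least one event.
- Weekly hazard: h = −ln(1 − p)/24
- Risk at 28 weeks: p28 = 1 − (1 − p)·exp(−4·k·h), where k is the off-drug to on-drug hazard ratio
- Shift in the BID–QD difference, for otherwise identical regimens: (p28 − p) × g, where g is the between-arm gap in the share of patients followed to Week 28
- Scale: 90% half-width = 1.645·√(2p(1 − p)/30)

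**Worked case, p = 70%, k = 1.** h = 1.204/24 = 0.0502. p28 = 1 − 0.30·exp(−0.2007) = 75.5%, a rise of 5.45 points. With roll-over of 90% in one arm and 60% in the other, g = 0.30 and the shift is 0.30 × 5.45 = 1.6 points.

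**Results with k = 1** (shifts in percentage points):

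| 24-week risk | 28-week risk | Rise | Shift, g = 0 | g = 0.20 | g = 0.30 | g = 0.50 | Patients of 30 at g = 0.30 | 90% half-width |
|---|---|---|---|---|---|---|---|---|
| 20% | 22.9% | 2.9 | 0 | 0.6 | 0.9 | 1.5 | 0.3 | 17.0 |
| 50% | 55.5% | 5.5 | 0 | 1.1 | 1.6 | 2.7 | 0.5 | 21.2 |
| 70% | 75.5% | 5.5 | 0 | 1.1 | 1.6 | 2.7 | 0.5 | 19.5 |

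The rise peaks near a 24-week risk of 60%: 1 − 0.40·exp(−0.1527) = 65.7%, a rise of 5.7 points, or 1.7 points at g = 0.30. So 1.6 to 1.7 is the ceiling for that gap when k = 1.

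**Sensitivity to k.** At g = 0.30 and the three tabulated risks, halving the off-drug hazard (k = 0.5) gives 0.4 to 0.9 points. Doubling it (k = 2) gives 1.7 to 3.1 points.

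**With the window closed at Week 24/ET**, every completer has 24 weeks and the roll-over shift is zero whatever the values of p, k and g.

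**The case against.** The strongest case against has four parts.

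1. *The change is disclosed, and the protocol is not of one mind.* SAP 3.4 names the rule it replaces, and the SAP states that it precedes database lock and unblinding. Protocol 10.1 was already open-ended. This stands: nothing was removed silently. But disclosure does not equalise observation time, and two conflicting protocol definitions are a reason for the SAP to fix one end point.

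2. *The comparison is between randomised arms.* A reader might infer that the open window necessarily confounds it with roll-over. The documents do not support that. Bias needs a difference between arms in roll-over or Week 28 attendance, and nothing in them shows or predicts one. Nor does every patient who skips the extension add four weeks: the visit can be waived or missed. For early terminators, Protocol 10.5 runs recording to the final study visit, while 10.6 ends reporting at the final visit or early termination.

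3. *The effect is small.* In the main scenarios it is about half a patient per arm or less, in a descriptive analysis. This stands and limits the weight of the point. By-patient listings with study days would also let a reader pick out late events, though not from the summary tables.

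4. *Closing the window does not make observation equal for all.* Early terminators still have shorter windows. True; the fix removes the roll-over artefact among completers, not every difference.

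A second tempting inference is that a serious event early in the extension counts against the randomised regimen, because Protocol 10.6 has a 30-day tail with no roll-over exception. The text does not establish this. It does not say how the period applies to a patient who continues dosing in another study, and Protocol 10.6.1 describes post-dose reporting more narrowly, for events the investigator considers caused by study drug. It is an ambiguity to reconcile, not a demonstrated misattribution.

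**Conclusion.** The point holds in conditional form. The SAP drops the end of the window set in Protocol 11.4.4. Crude TEAE percentages then combine 24-week windows with windows of up to 28 weeks, and the difference in length depends partly on a choice made after randomisation. The certain consequence is that on-drug and off-drug events are mixed in one table. Bias in the BID–QD comparison is possible but depends on roll-over or Week 28 attendance differing by regimen.

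Its likely size is small: zero with equal roll-over, and roughly 1 to 2 points with a 30-point gap at a constant event rate. These figures rest on assumed risks, an assumed gap, and all non-roll-over patients attending Week 28. They do not allow for patients who decline the extension being more prone to events than others. The point does not threaten the trial's conclusions, but it is worth correcting because the artefact is avoidable at little cost.

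**What to change.** In SAP 13.1:

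- Present the between-regimen TEAE tables, or at least an added set, limited to onset from first dose through Week 24 or the ET visit, as in Protocol 11.4.4. Update SAP 3.4 to match and note the conflict with Protocol 10.1.
- Show later events in a separate post-treatment table.
- State that events on or after the first extension-study dose are not counted in this study's tables.
- Report roll-over and Week 28 attendance by arm, so that readers can see whether observation differed.

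Separately, reconcile Protocol 10.5, 10.6 and 10.6.1 on when adverse-event reporting ends after early termination and how the 30-day serious-event period applies to roll-over patients.

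The cost is SAP wording, one additional table (or a parallel set, if the open-ended tables are kept) and two attendance counts, using dates already collected. Off-drug events leave the main table but stay visible in their own. Early terminators still have shorter windows, which a footnote should say.

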### **Clinical Laboratory**

Clinical laboratory variables will be presented in 3 ways. First, change from Baseline to each scheduled assessment will be summarized descriptively. Baseline will be defined as the laboratory value obtained before the first dose of study drug on Day 1; if Day 1 values are unavailable, then values obtained at the Screening Visit will be used.

Second, treatment-emergent potentially clinically significant (PCS) laboratory values will be identified. Potentially clinically significant values are defined as those that meet Grade 3 or Grade 4 toxicity criteria from the CTCAE criteria. Treatment-emergent PCS laboratory values are those in which the baseline value is not PCS and the post-baseline value is PCS.

Third, treatment-emergent PCS laboratory values that result in dose interruption will also be identified.

The mean change from Baseline to each scheduled assessment will be summarized descriptively by dosing regimen for each clinical laboratory variable specified in this protocol.

Concert Pharmaceuticals, Inc.

The number and percentage of patients with Abnormal, clinically significant laboratory values (per Investigator judgment) and the number and percentage of patients with treatment-emergent PCS laboratory values will be summarized by dosing regimen for each clinical laboratory variable.

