Frequency and percentage of patients who experienced TEAE will be further broken down by highest severity (mild, moderate, and severe). TEAE with severity of life-threatening and fatal will be reported under the severe intensity category while TEAE with an unknown/missing severity will be considered as severe. A patient experiencing multiple TEAEs within the same SOC will be counted only once for that SOC under the highest severity. Similarly, a patient experiencing multiple TEAEs within the same PT will be counted only once for that PT under the highest severity.

Listings of all AEs, all AEs leading to death, all serious AEs, all TEAEs leading to study drug discontinuation and all TEAEs leading to study discontinuation will be provided.

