13.2 Clinical Laboratory

Descriptive statistics will be presented by dosing regimen at Baseline and each post-Baseline visit for data related to chemistry, hematology, and lipids tests. Change from Baseline values will also be presented at each post-Baseline visit.

Separate listings will be provided for abnormal (low or high) chemistry (including lipids) and hematology laboratory results. Clinical laboratory results that fall outside the central laboratory reference range will be interpreted by the Investigator as Abnormal, not clinically significant (NCS) or Abnormal, clinically significant (CS). Abnormal, NCS and Abnormal, CS laboratory values will be flagged in the by-subject data listings.

Additionally, treatment-emergent potentially clinically significant (PCS) laboratory values will be identified. Potentially clinically significant values are defined as those that meet Grade 3 or Grade 4 toxicity criteria from the common terminology criteria for AEs (CTCAE) criteria. Treatment-emergent PCS laboratory values are those in which the Baseline value is not PCS and the post-Baseline value is PCS. Frequency and percentage of patients with treatment-emergent PCS laboratory values at any time on treatment will be summarized by dosing regimen for each clinical laboratory variable Frequency and percentage of patients with treatment-emergent PCS laboratory values will also be summarized by dosing regimen and post-Baseline visit for each clinical laboratory variable.

Line plots of means (+/- SEM) in laboratory value over time by dosing regimen will be presented for each hematology parameter of interest (i.e., hemoglobin, absolute neutrophils count, platelets, and reticulocytes).

	STATISTICAL ANALYSIS PLAN, Final v1.0
Protocol Number CP543.2003	Sponsor: Concert Pharmaceuticals, Inc.

Separate listings of all data for chemistry, hematology, lipids, serum pregnancy, serology, and other laboratory tests will also be provided. Treatment-emergent PCS laboratory values that result in dose interruption will be identified in these listings.

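### The SAP does not tabulate hematologic toxicity by action threshold, or dose interruption by cause or length, for each regimen, although comparing tolerability is part of the primary objective

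*SAP*

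**What the plan says.** **Objective and action limits.** SAP Section 2 places tolerability beside efficacy in the primary objective. Protocol 8.2, Table 3, sets the hematologic limits for interrupting drug: neutrophils below 1 x 10^9/L, hemoglobin below 10 g/dL in women and 11.5 g/dL in men, and platelets below 75 or above 750 x 10^9/L.

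**Laboratory values.** Protocol 11.4.4 asks for two counts by regimen and variable. One is of treatment-emergent potentially clinically significant (PCS) values. The other is "The number and percentage of patients with Abnormal, clinically significant laboratory values (per Investigator judgment"). SAP 3.4 removes the second: "This summary has been replaced by shift tables from Baseline to the worst post-Baseline result", graded low, normal or high by the central laboratory, with a reference to 13.2. SAP 13.2 gives by-visit statistics ("Change from Baseline values will also be presented at each post-Baseline visit"), PCS counts, mean plots for four hematology parameters, and listings. For PCS it says: "Potentially clinically significant values are defined as those that meet Grade 3 or Grade 4 toxicity criteria".

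**Adverse events.** Among its by-regimen TEAE tables, Protocol 11.4.4 lists "Adverse events that result in study drug dose interruption by system organ class and preferred term", and a matching table for discontinuation of study drug. The protocol synopsis also requires a by-patient listing of events leading to interruption. SAP 13.1 keeps one overall count and percentage for each. Its listings cover all AEs, deaths and serious AEs, and then "all TEAEs leading to study drug discontinuation and all TEAEs leading to study discontinuation will be provided".

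**Exposure.** Protocol 11.4.3 subtracts interruptions from days on drug. SAP 3.4 declares the opposite, "dose interruptions will not be excluded from the duration of exposure to the study drug", and SAP 11 computes last dose date minus first dose date plus 1.

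**The concern.** The study manages hematologic toxicity by interrupting or stopping drug, so who was interrupted, for what, and for how long is a direct measure of tolerability. Each of the three summaries that would show this by regimen has been thinned. One is replaced by a table that the named section does not describe. One is dropped without being declared, although SAP Section 1 says that changes from protocol-specified analyses will be documented. One is redefined so that interrupted days no longer reduce the result. With about 30 patients per arm, a handful of interruptions could be the main tolerability contrast. A reader of the tables could then see how many patients had an event leading to interruption, but not which events, which limits were crossed, or how many days were lost.

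**Working it through.** The plan states no figure on this point, so there is none to reproduce. The check is a comparison of the texts, then short arithmetic on exposure.

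**Step 1. Outputs side by side.**

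| Output | Protocol | SAP | Declared in SAP 3.4? |
|---|---|---|---|
| Patients with investigator-judged clinically significant laboratory values, n (%) | Required (11.4.4) | Flagged in listings only | Yes |
| Shift tables, Baseline to worst value | Not required | Announced in 3.4, absent from 13.2 | Yes, as the replacement |
| Patients with Grade 3/4 PCS values, n (%) | Required (11.4.4) | Kept (13.2) | No change |
| PCS values causing interruption | To be identified (11.4.4) | Identified in listings (13.2) | No change |
| TEAEs leading to interruption, by SOC and preferred term | Required (11.4.4) | Overall n (%) only (13.1) | No |
| TEAEs leading to discontinuation of drug, by SOC and preferred term | Required (11.4.4) | Overall n (%) and a listing (13.1) | No |
| Listing of AEs leading to interruption | In the synopsis; not in the 11.4.4 listing sentence | No dedicated listing | No |
| Days on drug net of interruptions | Required (11.4.3) | Replaced by first-to-last-dose duration (11) | Yes |

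The PCS count is defined by CTCAE grade and not by Table 3. Neither document plans a count of patients meeting a Table 3 limit.

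**Step 2. Exposure.** Inputs: 24 weeks of treatment (protocol synopsis); single interruptions of up to 21 consecutive days allowed (Protocol 8.2). The patient is treated to Day 168.

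- SAP exposure = last dose date − first dose date + 1 = 24 × 7 = 168 days.
- Protocol exposure = 168 − interrupted days.

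| Interrupted days | SAP | Protocol | SAP / protocol |
|---|---|---|---|
| 7 | 168 | 161 | 1.043 (+4.3%) |
| 14 | 168 | 154 | 1.091 (+9.1%) |
| 21 | 168 | 147 | 1.143 (+14.3%) |

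This applies only when dosing resumes, because the SAP interval ends at the last dose.

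**Step 3. Effect on an arm mean.** One 21-day interruption among 30 patients: 21 / 30 = 0.7 day, and 0.7 / 168 = 0.4%.

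**Step 4. Whether compliance shows it.** Each dose is two tablets every 12 hours (Protocol 8.1, SAP 3.2), so 4 per day.

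- Planned: 168 × 4 = 672 tablets. Taken with 21 days off: 147 × 4 = 588. Compliance = 588 / 672 = 87.5%.
- Mean compliance falls, but the patient stays in the SAP's 80% to 120% category. Leaving it needs more than 0.20 × 168 = 33.6 days off, hence 34.
- As printed, SAP 11 multiplies exposure days by 2 tablets per dose. Full dosing then gives 672 / 336 = 200%, and the interrupted patient 588 / 336 = 175%. The denominator needs correcting before compliance can serve this purpose.

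**The case against.** The strongest reply is that little is lost. Protocol 11.4.4 has clinically significant laboratory values reported and summarized as AEs, so they reach the by-regimen TEAE tables. SAP 13.1 keeps overall counts for interruption and discontinuation. SAP 13.2 keeps means, changes, hematology plots and listings. The Grade 3/4 rule is the protocol's own. The exposure change is open and reasoned, and a patient who does not resume has a shorter exposure. Section 3.4 is part of the SAP and describes the shift tables, and output layouts sit in a separate document (SAP Section 5). The interruption listing is asked for only in the synopsis. The protocol also reports no hematologic dose interruptions so far at 12 mg BID in the earlier Phase 2 study.

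Most of this stands, and it rules out stronger readings:

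- A reader might infer that toxicity prompting Table 3 action becomes largely invisible, or that a real difference could appear as no PCS values and equal exposure. The remaining outputs listed above do not support that. The TEAE route does depend on investigator judgment, and it does not link an event to an interruption.
- A reader might try to size the gap as the hemoglobin range between a Grade 3 cut-off and the Table 3 limits. The documents give no CTCAE cut-offs and no expected frequencies, so no such figure is supported.
- A reader might infer that the shift tables have been abandoned. The text shows only that 13.2 does not contain what 3.4 says is there.

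The reply does not supply the undeclared SOC and preferred-term tables, the shift-table specification, or any summary of interrupted days.

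**Conclusion.** The point holds in a limited form. Followed as written, the SAP omits two protocol-required by-regimen tables without declaring it. It refers to a replacement laboratory table that its safety section does not specify. It also leaves no summary of interrupted or net dosed days. What is missing is tabulation by threshold, cause and length; the fact of interruption is still counted.

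The size is modest. Reported exposure is 14.3% above the protocol's measure for a patient with one 21-day interruption and otherwise full dosing to Day 168. It is about 0.4% on an arm mean if one patient in 30 is affected; repeat interruptions or more affected patients would raise this. The documents give no basis for predicting how many patients will meet a Table 3 limit. The change is worth making because tolerability is in the primary objective, the arms are small and the remedy is cheap. Nothing here questions the Table 3 limits or how patients are managed.

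**What to change.** Amend the SAP before database lock:

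- **13.2:** write in the Baseline-to-worst shift tables announced in 3.4. Add, by regimen, the number and percentage of patients meeting each existing Table 3 limit at any time on treatment.
- **13.1:** restore the SOC and preferred-term tables for TEAEs leading to interruption and to discontinuation of study drug, and the synopsis listing of events leading to interruption. Reconcile the synopsis with the listing sentence in Protocol 11.4.4. If any of these outputs is deliberately left out, say so in 3.4.
- **11:** beside the overall duration, report net dosed days, the number of patients interrupted and the total interrupted days, by regimen. Correct the tablets-per-day term in the compliance denominator.

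The cost is SAP wording and a few extra tables. Laboratory results, the action taken for each AE and dosing records are already to be collected, so sites have nothing new to do.
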